### 10.5.2 Analyses of Exploratory Endpoints

## **10.6 Safety Analyses**

### **10.6.1 Analyses of Primary Endpoints**

The subject incidence of DLT based on CRF will be summarized as a binary variable using the DLT Analysis Set by calculating the frequency, percentage, and exact 95% CI.

### **10.6.2 Adverse Events**

The Medical Dictionary for Regulatory Activities (MedDRA) version **23.0** or later will be used to code all adverse events (AE) to a system organ class and a preferred term. The CTCAE version 4.0 will be used to grade severity of adverse events. In general, events with missing IP relatedness, seriousness, or CTCAE severity grades are included in the analysis of treatment emergent AE as long as the event meets the criteria for a TEAE. However, analyses of treatment-related, SAE, or grade 3 or higher, or combination thereof will exclude events with missing relatedness, seriousness, and severity grades, respectively.

The analyses for AEs will include TEAEs (ie, occurring in the treatment period) unless otherwise specified. The subject incidence of TEAEs will be summarized for all AEs, serious AEs, AEs leading to withdrawal of investigational product, grade 3 or 4 AEs, and fatal AEs. The subject incidence of all treatment-related AEs, serious AEs, AEs leading to withdrawal of investigational product, grade 3 or 4 AEs, and fatal AEs will be tabulated by system organ class (SOC) and preferred term in descending order of frequency. A listing of fatal AEs will be provided. A listing of all SAEs reported in the clinical database with an event onset from consent will be provided with onset reported relative to the first and most recent dose of study therapy and identification as a TEAE.

Subject incidence of DREs (disease-related events), fatal disease related events, serious disease-related events, and disease-related events leading to withdrawal from study will be tabulated by system organ class and preferred term.

Treatment-related AEs reported in long term follow-up will be summarized in this study and analyzed at a program-level.

Potential or known unintended exposure to talimogene laherparepvec, related suspected signs or symptoms, and detection of exposure to talimogene laherparepvec in a subject's household member, caregiver, or healthcare provider will be reported to Amgen. Exposures, signs or symptoms will be summarized in this study and analyzed at a program-level.

### **10.6.3 Laboratory Test Results**

Shifts in grades of safety laboratory values between the baseline and the worst on-study value will be tabulated. For a list of laboratory measurements see protocol Section 7.4 Table 3. Subject incidence of potential hepatotoxicity as identified by the Hy's Law criteria (FDA guidance for Industry Drug Induced Liver Injury: pre-marketing evaluation, July 2009) as well as confirmed DILI events as reported by investigators will be presented.

### **10.6.4 Vital Signs**

Descriptive statistics will be presented for systolic/diastolic blood pressure, heart rate, respiratory rate, and temperature for baseline, each post-baseline visit, and change from baseline.

### **10.6.5 Lansky Play Scale and Karnofsky Performance Status**

Performance status scores will be summarized at each assessed time point. The change in scores from baseline to each assessed time point will also be summarized.

#### **10.6.6 Physical Measurements**

Height and weight will be summarized at each assessed time point. The change in weight from baseline to each assessed time point will also be summarized as a difference in original units of measurement and as percentage difference.

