3.5 Estimated Study Duration

3.5.1 Study Duration for Subjects

The duration of screening for each subject will be approximately 28 days (1 month). The duration of treatment is anticipated to be 9 months. All subjects will complete a safety follow-up visit approximately 30 (+ 7) days after the last dose of study treatment. After the safety follow-up visit subjects will enter the long-term follow-up. During this period, subjects will be followed for survival for **and use of subsequent anticancer therapies every 12 weeks (± 28 days) from the safety follow-up visit until death, subject or legally acceptable representative withdraws full consent/assent, or up to** approximately 24 months after the last subject is enrolled in the study, **whichever occurs first**. The study duration for an individual subject is expected to be approximately 35 months.

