4.1 Inclusion Criteria

- 101 Subject's legally acceptable representative has provided informed consent/assent when the subject is legally too young to provide informed consent/assent and the subject has provided written assent based on local regulations and/or guidelines prior to any study-specific activities/procedures being initiated.
- 103 Should be willing to submit local HSV-1 serostatus within 28 days prior to enrollment.
- 106 Subject must be a candidate for intralesional injection, defined as one or more of the following:
- at least 1 injectable lesion ≥ 10 mm in longest diameter
 - multiple injectable lesions that in aggregate have a longest diameter of ≥ 10 mm
- NOTE: visceral lesions are not eligible for injection. Additionally, bone lesions are not eligible for injection unless there is a soft tissue component that is amenable to injection.
- 108 Life expectancy > 4 months from the date of enrollment.
111. Male or female subjects 2 to ≤ 21 years of age at the time of informed consent/assent.
112. Histologically or cytologically confirmed non-CNS solid tumor that recurred after standard/frontline therapy, or for which there is no standard/frontline therapy available.
113. Presence of measurable or non-measurable lesions as defined by irRC-RECIST

Approved

114. Performance status:
- Karnofsky $\geq 70\%$ for 12 to ≤ 21 years of age.
 - Lansky play scale $\geq 70\%$ for children 2 to < 12 years of age.
116. Female subject of childbearing potential should have a negative urine or serum pregnancy test within 72 hours prior to dosing. If urine test is positive or cannot be confirmed as negative, a serum pregnancy test will be required. A female is considered of childbearing potential (FCBP), ie, fertile, following menarche and until becoming post-menopausal unless permanently sterile. Permanent sterilisation methods include hysterectomy, bilateral salpingectomy and bilateral oophorectomy.
- 117.
118. Adequate organ function as defined as follows:
- Hematological (without need of hematopoietic growth factor and/or transfusion support within **7 days from screening assessment**)
 - absolute neutrophil count (ANC) $\geq 1.0 \times 10^9/L$
 - platelet count $\geq 75 \times 10^9/L$
 - hemoglobin ≥ 8 g/dL
 - Renal

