^d Subjects undergoing talimogene laherparepvec treatment beyond week 32 should continue general study assessments and local laboratory tests until the end of treatment (vital signs, recording of concomitant medications and review of adverse events, disease-related events and serious adverse events, [REDACTED], physical exam, body weight and performance status every fourth cycle and chemistry and hematology every second cycle). Exposure of subject's household member or caregiver and healthcare provider should continue to be checked at every cycle.

^e Vital signs (blood pressure, heart rate, respiration rate, and temperature) to be collected predose.

^f Karnofsky performance status will be used for subjects aged 12 to \leq 21 years; Lansky play scale will be used for subjects aged 2 to < 12 years.

^g Only anticancer therapies will be collected/recorded every 12 weeks during the long-term follow-up.

^h Talimogene laherparepvec related adverse events.

ⁱ Female subjects of childbearing potential only. A female is considered of childbearing potential (ie, fertile), following menarche and until becoming post-menopausal unless permanently sterilized. Permanent sterilization methods include hysterectomy, bilateral salpingectomy and bilateral oophorectomy.

^j To be performed within 72 hours prior to dosing.

^k Blood sample for HSV serostatus will be performed at a local laboratory at screening and at a central laboratory thereafter.

^m Blood draw for real-time polymerase chain reaction (qPCR) testing of talimogene laherparepvec DNA will be performed at the following time points:

- day 1 (prior to and approximately 1 hour [\pm 15 minutes] and 4 hours [\pm 30 minutes] after talimogene laherparepvec administration), day 2 approximately 24 hours [\pm 30 minutes] after talimogene laherparepvec administration, day 8 (\pm 2 days), day 22 (prior to and approximately 1 hour [\pm 15 minutes] and 4 hours [\pm 30 minutes] after talimogene laherparepvec administration), day 23 approximately 24 hours [\pm 30 minutes] after talimogene laherparepvec administration, day 29 (\pm 2 days), day 36 (\pm 2 days) prior to dosing, and day 50 (\pm 2 days) prior to dosing.

Approved

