^s Radiologic imaging of all sites of disease must be performed (including imaging of the brain when clinically indicated). For subjects remaining on treatment with talimogene laherparepvec beyond week 32, radiologic imaging should continue every 12 weeks until confirmed progressive disease per modified irRC-RECIST or start of new anticancer treatment. All study imaging should be performed according to the calendar and not adjusted for any cycle initiation delays.

^t Subjects who are in complete response and no longer have injectable lesions will enter the 30-day safety follow-up and continue to have tumor assessments every 12 weeks for up to 24 months.

^u For subjects with metastatic melanoma, clinical tumor assessments, including clinical measurements of cutaneous, subcutaneous, or nodal measurement by caliper should be measured at baseline assessment, as well as subsequent scheduled tumor assessments. Measurements should continue every 12 weeks until confirmed progressive disease per modified irRC-RECIST or start of new anticancer treatment.

^v Clinically applicable tumor markers appropriate for the tumor type include, but are not limited to, serum alpha fetoprotein, serum beta human chorionic gonadotropin and urine for homovanillic acid/vanillylmandelic acid. Tumor marker measurement is required to confirm CR if screening level of tumor marker was above the ULN and criteria for CR per modified irRC-RECIST guidelines are met.

^w Treatment may continue for up to 24 months depending on response to and tolerance of talimogene laherparepvec.

^x If applicable.

Approved

Refer to the applicable supplemental (eg, laboratory, imaging) manuals for detailed collection and handling procedures.

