7.3.6 Physical Measurement

Height in centimeters and weight in kilograms should be measured.

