10.4.2 Secondary Endpoints

Efficacy Endpoints:

ORR, DOR, TTR, TTP, PFS, and OS will be summarized in the overall population. ORR will be summarized with an associated exact 95% CI using the safety analysis set and excluding subjects without baseline measurable disease, if applicable. DOR among responders, TTR, TTP, PFS and OS will be estimated using the Kaplan-Meier method.

Safety Endpoints

Subject incidence of treatment-emergent and treatment-related adverse events will be summarized. **Treatment-emergent adverse events are defined as any adverse event occurring after first dose through 30 days after last dose of talimogene**

laherparepvec. Treatment-related adverse events are defined as treatment-emergent adverse events which are considered to be related to the treatment of talimogene laherparepvec, as determined by the investigator. Medical Dictionary for Regulatory Activities (MedDRA) will be used to code adverse events to a system organ class (SOC) and a preferred term within the SOC. The CTCAE version 4.0 will be used to grade severity of adverse events. In addition, clinically significant laboratory changes and clinically significant changes in vital signs will be summarized with descriptive statistics.

Subject incidence of all disease-related events, fatal disease-related events, serious disease-related events, and disease-related events leading to withdrawal from study drug will be provided.

[figure not shown]
A summary of deaths after initiation of the study through 30 days since the last dose of talimogene laherparepvec will be provided.

Summary statistics will also be provided for concomitant medications, dose delay, study drug discontinuation, overall exposure, and Karnofsky performance status and Lansky play scale.

[figure not shown]
Potential or known unintended exposure to talimogene laherparepvec, related suspected signs or symptoms, and detection of exposure to talimogene laherparepvec in a subject's household member, caregiver, or healthcare provider will be reported.

Summary statistics will be provided for vital signs, physical measurements and laboratory data. Details of the analysis will be provided in statistical analysis plan.

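### Weight change is planned only in kilograms and percent, so in subjects who are still growing a failure to gain weight can read as no change

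*SAP*

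**What the plan says.** The protocol (10.4.2) commits only to this: "Summary statistics will be provided for vital signs, physical measurements and laboratory data". It leaves the detail to the SAP.

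SAP 10.6.6 supplies that detail in two sentences. The first is "Height and weight will be summarized at each assessed time point". The second adds the change in weight from baseline, "summarized as a difference in original units of measurement and as percentage difference". Under SAP 10.1, descriptive summaries are given for all subjects and by cohort, with mean, standard deviation, median, quartiles, minimum and maximum for continuous variables.

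The population is "Male or female subjects 2 to ≤ 21 years of age at the time of informed consent/assent" (Protocol 4.1), split into cohort A1 (12 to 21 years) and cohort B1 (2 to under 12). On duration, Protocol 3.5.1 says "The duration of treatment is anticipated to be 9 months", and a footnote to Protocol Table 3 says "Treatment may continue for up to 24 months depending on response to and tolerance of talimogene laherparepvec".

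Table 3 schedules body weight on Day 1, on Days 50, 106, 162 and 218, and at safety follow-up. Beyond week 32 another footnote continues "physical exam, body weight and performance status every fourth cycle". Height is scheduled on Day 1 only.

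Neither document mentions a z-score, a percentile, an expected-growth reference or any other growth-standardized measure.

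**The concern.** A change from baseline in kilograms or percent is naturally read against zero. In a growing child zero is the wrong reference, because the expected change is a gain that depends on age and sex. A child whose weight stays flat for months reports 0% and looks unaffected. A child who loses weight after an earlier gain can still report a positive change.

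A randomized comparison would largely cancel expected growth between arms. Here every subject receives talimogene laherparepvec, so nothing in the design does that. Reporting by cohort helps only in part: B1 covers ten years of childhood, and A1 can mix growing adolescents with fully grown young adults.

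At stake is the reading of one of the few objective tolerability measures that is repeated through treatment. Other parts of the plan do allow for age: several laboratory eligibility limits (Protocol 4.1) use an upper limit of normal for age, and performance status uses a different scale in each age group.

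**Working it through.** There is no sample size, power or event count behind this section of the SAP, so there is no planned figure to reproduce. The check is what a reported 0% change would mean.

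**Inputs from the documents**
- Scale of the summary: kilograms and percent (SAP 10.6.6).
- Age 2 to 21 years (Protocol 4.1).
- Treatment anticipated for 9 months (Protocol 3.5.1), 24 months at most (Protocol Table 3).
- Last weight column in Table 3 before follow-up: Day 218, which is 217 days after Day 1, or 217/365 = 0.59 year.

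**Assumed inputs** (the documents give none)
- Expected gain g: 1 to 3 kg per year for small children, 1 to 5 kg per year for a growing adolescent, 0 for a subject who has stopped growing.
- Baseline weights W of 15, 20 and 50 kg, as illustrations.

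**Formulas**
- Expected gain by time t: E = g × t.
- If the reported change is 0%, the shortfall from expected weight is E / (W + E).

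**One case in full.** For a 15 kg child at Day 218:
- g = 1: E = 0.59 kg and 0.59/15.59 = 3.8%.
- g = 3: E = 1.78 kg and 1.78/16.78 = 10.6%.

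**Shortfall behind a reported 0% change**

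| Baseline weight, assumed gain | Day 218 | 9 months | 24 months (maximum) |
|---|---|---|---|
| 15 kg, 1 to 3 kg/year | 3.8 to 10.6% | 4.8 to 13.0% | 11.8 to 28.6% |
| 20 kg, 1 to 3 kg/year | 2.9 to 8.2% | 3.6 to 10.1% | 9.1 to 23.1% |
| 50 kg, 1 to 5 kg/year | 1.2 to 5.6% | 1.5 to 7.0% | 3.8 to 16.7% |
| Any weight, 0 kg/year | 0% | 0% | 0% |

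E is 0.59, 1.78 and 2.97 kg at Day 218 for 1, 3 and 5 kg per year; 0.75, 2.25 and 3.75 kg at 9 months; and 2, 6 and 10 kg at 24 months.

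**Does a real deficit always disappear?** Take a 15 kg child who is 8% below expected weight at Day 218.
- g = 1: 0.92 × 15.59 = 14.34 kg, a reported change of (14.34 − 15)/15 = −4.4%. The loss is visible, though understated.
- g = 3: 0.92 × 16.78 = 15.44 kg, a reported change of +2.9%. The deficit reads as a gain.

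So the direction is certain for anyone still growing. Whether a given deficit is hidden or only reduced depends on the growth rate.

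**Height.** Protocol 7.3.6 says "Height in centimeters and weight in kilograms should be measured", but Table 3 places height on Day 1 only. The SAP's summary of height by time point is therefore a baseline summary, and no change in height can be derived from the scheduled data.

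**The case against.** The case against is substantial, and much of it stands.

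- Weight is not an endpoint. It is not named among the DLT criteria, and Protocol 6.2.1.2 makes dose depend on tumor size rather than on weight. Kilograms and percent describe correctly what was measured. This stands, and it sets the level of the point.
- A reader might infer that the plan hides weight loss in general. It does not. Any fall below baseline appears as a negative change; weight itself is summarized at every assessed time point with its minimum and maximum; and evident weight loss can be reported as an adverse event. What can be masked is failure to gain, or loss offset by growth.
- A reader might infer that most subjects are affected. The documents do not support that. At Amendment 3, 10 of the 11 enrolled subjects were in A1 and further enrolment was expected mainly there. Protocol 2.4 puts diagnosis of the likely tumors at around 15 years, with recurrence 1 to 5 years later. An unknown share of A1 may have stopped growing.
- A reader might take the 24-month column as typical. It is the maximum. Nine months is anticipated, and treatment also ends at confirmed progression.
- A reader might infer that impaired height growth is at issue, or that the SAP contradicts Table 3 on height. Neither follows: the scheduled data cannot show height growth at all, and one scheduled height simply gives one assessed time point.
- A healthy-child reference is not a clean no-effect value for children with recurrent tumors, and a single arm cannot separate disease from drug. This is true, but zero change is a poorer reference for a growing child, and the z-score would be added, not substituted.

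**Conclusion.** The point holds in a limited form. For subjects still growing, the planned weight summary uses a scale on which no change is not the expected result. Failure to gain weight, or loss offset by growth, can therefore pass unnoticed.

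The size rests wholly on the assumed growth rates. At 1 to 3 kg per year, 0% by Day 218 in a 15 kg child stands for about 4 to 11% below expected weight. The shortfall is smaller in adolescents, and zero once growth has stopped. The number of subjects concerned is likely to be small: B1 had one subject at Amendment 3 and has no required minimum, and the growing share of A1 is not known.

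This is a minor improvement to one descriptive safety table. It has no bearing on the DLT endpoint, the rules for opening cohorts or de-escalating, or the sample size.

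**What to change.** Amend SAP 10.6.6 as follows.

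- Add the change from baseline in weight z-score for age and sex, by cohort, against one named growth reference used for all sites.
- State how the oldest subjects are handled, for example with the reference's upper-age values.
- State how age at each visit is derived. Protocol 11.3 puts age at enrollment on the CRF and allows date of birth only where permitted, so some ages may be approximate.
- List individual z-score changes. B1 will be small, and a listing will say more there than a mean.
- Keep the kilogram and percent summaries.
- State that height is summarized at baseline only, because Table 3 schedules it on Day 1 only, and make no claim about height growth.

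The cost is SAP wording and a short program. Age, sex and weight are already collected, so no visit or procedure is added. The drawbacks are that a reference has to be chosen and that it may fit the oldest subjects less well.

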#### **10.6.7 Electrocardiogram (ECG)**

The ECG measurements from this clinical study were performed as per standard of care for routine safety monitoring, rather than for purposes of assessment of potential QTc effect. Since these evaluations may not necessarily be performed under the rigorous conditions expected to lead to meaningful evaluation of QTc data; neither summaries nor statistical analyses will be provided, and these data would not be expected to be useful for meta-analysis with data from other trials.

#### **10.6.8 Exposure to Investigational Product**

Summary statistics for exposure to talimogene laherparepvec, including total doses administered, total volume administered, duration from the first to the last administration of talimogene laherparepvec, and the average volume received by subject per visit will be provided and will be separated by the first (concentration of  $10^6$  PFU/mL) and subsequent doses (concentration of  $10^8$  PFU/mL or  $10^6$  PFU/mL). Subject incidence rate and reasons for IP delay, dose change, withdrawal and/or injections with  $\leq 4$  mL will be tabulated.

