6.2.1.1 Dosage, Administration, and Schedule

Talimogene laherparepvec must be prepared and administered by a qualified healthcare professional. Subjects should be assessed clinically for adverse events/toxicity prior to each dose using the CTCAE version 4 ([Appendix A](#)). Complete blood count with differential and chemistry panels including liver function laboratory tests (ALT, AST, and total bilirubin) should be obtained according to the Schedule of Assessments ([Table 3](#)) and the results should be checked before each treatment. Dosing will occur only if these test values are acceptable per [Section 6.2.1.2](#) and [6.2.1.3](#). Sedation can be used and the type and dose is up to the discretion of the investigator taking into consideration the subject's medical history, age, and site of disease. Additionally, use of pain medication (eg, acetaminophen/paracetamol/narcotic) or anti-anxiety medication (eg, benzodiazepine) as premedication to help decrease the pain or anxiety associated with the injection is acceptable and left to the discretion of the investigator. Because

flu-like symptoms are common adverse events experienced by HSV-seronegative subjects after talimogene laherparepvec treatment, premedication with the appropriate antipyretic and/or antiemetic medications prior to each talimogene laherparepvec treatment is strongly recommended to prevent the occurrence of these symptoms in the HSV-seronegative subjects. The type and dose will be up to the discretion of the investigator taking into consideration the subject's medical history and age.

Talimogene laherparepvec will be administered by intralesional injection only into injectable cutaneous, subcutaneous, nodal tumors, and other non-visceral tumors with or without image guidance. Talimogene laherparepvec must not be administered into tumor lesions in visceral organs.

The first dose of talimogene laherparepvec will be up to 4.0 mL of 10^6 PFU/mL administered on day 1. The second injection, up to 4.0 mL of 10^8 PFU/mL (or up to 4.0 mL of 10^6 PFU/mL for a dose de-escalated cohort), will be administered 21 (+ 3) days after the initial injection (ie, no sooner than day 22 but should not be delayed more than 3 days after the 21-day time point). All subsequent injections, up to 4.0 mL of 10^8 PFU/mL (or up to 4.0 mL of 10^6 PFU/mL for a dose de-escalated cohort), will be administered every 14 (\pm 3) days. The treatment cycle interval may be increased due to toxicity.

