The maximum volume of talimogene laherparepvec administered at any dose is 4.0 mL for any individual lesion and in any treatment.

The recommended volume of talimogene laherparepvec to be injected into the tumor(s) is dependent on the size of the tumor(s) and should be determined according to the injection volume guideline in [Table 2](#). It is recommended that each lesion should receive the maximum amount possible to inject due to tumor properties at each visit before moving on to the next lesion, using the prioritization model below and the injection volume guideline based on tumor size per [Table 2](#). The lesion site injected will be recorded on the CRF.

Approved

Table 2. Talimogene Laherparepvec Injection Volume Guideline Based on Tumor Size

Tumor Size (longest dimension)	Maximum Injection Volume
> 5.0 cm	4.0 mL
> 2.5 cm to 5.0 cm	2.0 mL
> 1.5 cm to 2.5 cm	1.0 mL
> 0.5 cm to 1.5 cm	0.5 mL
≤ 0.5 cm	0.1 mL

On each treatment day, prioritization of injections is recommended as follows:

1. any new injectable tumor that appeared since the last injection
2. by tumor size, beginning with the largest tumor
3. any tumor previously seen on tumor assessment that was too small to inject that has now become large enough to inject

Subjects will be treated with talimogene laherparepvec until subjects have achieved a complete response (CR), all injectable tumors have disappeared, confirmed progressive disease (PD) per modified irRC-RECIST, intolerance of study treatment, 24 months from the date of the first dose of talimogene laherparepvec, or need for alternative anti-cancer therapy, whichever occurs first. Due to the mechanism of action, subjects may experience growth in existing tumors or the appearance of new tumors prior to maximal clinical benefit of talimogene laherparepvec. Therefore, modified irRC-RECIST will be used instead of standard RECIST 1.1 ([Nishino et al, 2014](#)). Details can be found in [Appendix D](#).

The dose (total volume and concentration), lesion site, treatment start date, and lot number of talimogene laherparepvec are to be recorded on the CRF.

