6.2.1.3 Dosage Adjustments, Delays, Rules for Withholding or Restarting, Permanent Discontinuation

Talimogene laherparepvec treatment should be continued based on the potential benefit/risk assessment of the subject.

Dose reduction within a cohort for an individual subject who experience adverse events is not allowed. If in the course of administration of talimogene laherparepvec the subject cannot tolerate the full dose due to an injection-related adverse event, the total volume given should be recorded, and the reason for intolerance should be documented as an adverse event.

If a subject experiences any of the following treatment-related toxicities, administration should be delayed until the toxicity has resolved to at least CTCAE grade 1 or baseline:

- grade 2 or greater immune-mediated adverse events, with the exception of vitiligo
- grade 2 or greater allergic reactions
- any other grade 3 or greater hematologic or non-hematologic toxicity

If the subject requires corticosteroid dosing greater than that required for maintenance physiologic replacement therapy, talimogene laherparepvec dosing should be withheld.

If a subject demonstrates evidence of new or worsening CNS metastases, all study treatments should be withheld. Resumption of talimogene laherparepvec dosing should be left to the discretion of the investigator and discussed with the Amgen medical monitor.

If talimogene laherparepvec treatment is delayed by > 1 week, that dose will be deemed to have been missed and the subject will proceed to the next scheduled treatment visit.

If talimogene laherparepvec dosing is delayed by more than 6 weeks from the date of the planned dose due to the occurrence of an adverse event that is considered related to talimogene laherparepvec, the subject must be permanently withdrawn from talimogene laherparepvec treatment. If talimogene laherparepvec dosing is delayed by more than 6 weeks from the date of the planned dose for reasons other than treatment-related toxicity, the case must be reviewed by the Amgen medical monitor in conjunction with the investigator to determine if the subject can resume talimogene laherparepvec therapy. Reason for dose change of talimogene laherparepvec is to be recorded on CRF.

Talimogene laherparepvec will be permanently discontinued for subjects meeting any of the following criteria:

- Subject developed DLT during the DLT evaluation period.

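### SAP 10.6.8 counts injections of at most 4 mL, but 4.0 mL is the protocol maximum, so the incidence is 100% for compliant dosing and cannot separate full from incomplete injections (minor)

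*SAP*

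**What the plan says.** SAP 10.6.8 has two parts. The first is descriptive: "Summary statistics for exposure to talimogene laherparepvec, including total doses administered, total volume administered", together with duration and average volume per visit, separated into first and subsequent doses. The second is a table of "Subject incidence rate and reasons for IP delay, dose change, withdrawal and/or injections with" a volume of ≤ 4 mL. The sign is non-strict.

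Protocol 6.2.1.1 sets the ceiling: "The maximum volume of talimogene laherparepvec administered at any dose is 4.0 mL for any individual lesion and in any treatment". Doses are stated as upper limits, for example "The first dose of talimogene laherparepvec will be up to 4.0 mL". Within that limit, "The recommended volume of talimogene laherparepvec to be injected into the tumor(s) is dependent on the size of the tumor(s"), and Table 2 gives maxima of 4.0, 2.0, 1.0, 0.5 and 0.1 mL for five size bands.

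Protocol 6.2.1.3 does not allow dose reduction for an individual subject. It does cover the injection that cannot be completed because of an injection-related adverse event: "the total volume given should be recorded, and the reason for intolerance should be documented as an adverse event". It also requires the reason for a dose change to be entered on the CRF.

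**The concern.** The row stands beside delay, dose change and withdrawal, each with reasons. The natural reading, which the SAP does not state, is that it should show departures from full dosing. A threshold equal to the permitted maximum, with the maximum included, cannot do that.

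At stake is a direct view of how often an injection was cut short because the subject could not tolerate it. That bears on tolerability, which is part of the primary objective. Total and average volume do not supply it, because small tumors also produce low volumes.

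**Working it through.** The plan states no figure for this row, so there is none to reproduce. The check is logical, followed by an enumeration.

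**Inputs**
- Criterion: v ≤ 4 mL (SAP 10.6.8).
- Cap: v ≤ 4.0 mL per lesion and per treatment (Protocol 6.2.1.1).
- Table 2 maxima: 4.0, 2.0, 1.0, 0.5, 0.1 mL.
- Denominator: the safety analysis set, meaning subjects with at least one dose (SAP 7.2 and 10.1).

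**Step 1: the criterion as written.** The cap and the criterion are the same inequality. It does not matter whether an injection means one lesion or one visit, because the cap applies to both. Every subject in the denominator has at least one dose, so the incidence is n/n = 100%. A subject could escape the count only if every one of their injections exceeded the protocol maximum.

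**Step 2: would a strict sign work?** Take visits at the full Table 2 volume, with nothing withheld. For k lesions, visit total = min(4.0, sum of the Table 2 maxima). Enumerating all combinations of bands gives:

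| Lesions | Combinations | Flagged by ≤ 4 mL | Flagged by < 4 mL |
|---|---|---|---|
| 1 | 5 | 5 | 4 |
| 2 | 15 | 15 | 9 |
| 3 | 35 | 35 | 15 |
| 4 | 70 | 70 | 20 |
| 5 | 126 | 126 | 23 |
| 6 | 210 | 210 | 25 |

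For two lesions, five combinations contain a 4.0 mL band and one is 2.0 + 2.0, so 15 − 6 = 9 remain below 4.0 mL. These are counts of possible patterns, not expected proportions of visits. None of them involves an incomplete injection, so every flag in the last column is a false one for the purpose in question.

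**Step 3: three illustrative single-lesion injections.** The volumes given are assumed for illustration.

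| Case | Table 2 maximum | Given | ≤ 4 mL | < 4 mL | Intended volume not fully given |
|---|---|---|---|---|---|
| Lesion > 5.0 cm, completed | 4.0 mL | 4.0 mL | yes | no | no |
| Lesion of 2 cm, completed | 1.0 mL | 1.0 mL | yes | yes | no |
| Lesion > 5.0 cm, stopped for an adverse event | 4.0 mL | 2.0 mL | yes | yes | yes |

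The written criterion treats all three alike, and the strict sign still merges the second and third. Only the last column isolates the event that Protocol 6.2.1.3 describes.

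**The case against.** The strongest reply is that little is lost.

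- **The reasons are tabulated too.** They can vary with the data even when the incidence cannot. This stands. A reader might infer that the whole table is empty, and the documents do not support that. What is fixed at 100% is the incidence.
- **Intolerance is recorded elsewhere.** Protocol 6.2.1.3 has it documented as an adverse event, so it reaches the treatment-emergent summaries in SAP 10.6.2. It may also appear under dose change, although the documents do not say whether a partly given volume is coded that way. A reader might infer that the tolerability evidence disappears. It does not; what is missing is its link to the volume given.
- **The purpose of the row is inferred.** This also stands. But no purpose is served by an incidence that must equal 100%.
- **The sign may have been misread from the PDF.** This is unlikely, since the SAP shows < and ≤ as distinct signs elsewhere, for example in the age bands. It should be checked against the source file. If the strict sign was meant, the 100% result goes, but the mixing in Step 2 remains.

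A reader might also call the cut-short injection a within-subject dose reduction. The protocol does not: it disallows such reductions and treats this case as intolerance.

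**Conclusion.** The criterion is wrong as written, and the consequence is minor. For all protocol-compliant dosing the subject incidence is 100% by construction, so it cannot distinguish full from incomplete injections.

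This rests on the ≤ sign being correct in the source and on doses staying within the 4.0 mL maximum. The further conclusion, that a strict sign would not isolate incomplete injections, rests only on Table 2.

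The effect is confined to one descriptive exposure row. The DLT endpoint, the cohort rules and the total and average volume summaries are unaffected. It is tempting to see this as a one-symbol error, but Table 2 does not support that, because four of its five maxima are below 4.0 mL.

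**What to change.** Replace the ≤ 4 mL item in SAP 10.6.8 with two items:

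1. Subject incidence of injections where the intended volume was not fully given, by reason: injection-related adverse event under Protocol 6.2.1.3, or other.
2. Separately, injections below 4.0 mL because of tumor size under Table 2.

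The sources are the recorded total volume, the reason for dose change and the intolerance adverse event, all of which the protocol already asks for. Where lesion size at injection is available, the volume given can be compared with the Table 2 volume. Table 2 gives maxima, and Protocol 6.2.1.1 accepts that tumor properties may limit what can be injected. A shortfall against Table 2 therefore still needs its reason before it is read as intolerance.

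The cost is a reworded sentence and a revised table. The one uncertainty is the CRF, which is not among the documents: Protocol 6.2.1.1 does not list intended volume or lesion size at each injection among the recorded items, and tumor assessments are scheduled less often than injections. The sponsor should confirm that the fields support the split. If lesion size at injection is not captured, the split should rest on the recorded intolerance adverse event alone. No dose or clinical rule changes.
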